3.3.7. Drug safety measures

Adverse effects: In OPEN, we will measure possible adverse effects in a structured and standardised manner. As there are no existing guidelines concerning the use of antipsychotics in AN, we decided on the clinical outcome measures of adverse effects based on the World Federation of Societies of Biological Psychiatry (WFSBP) Guidelines for Biological Treatment of Schizophrenia [72].

- Physical examination:
 - Weight
 - Blood pressure (BP) and pulse
 - Body temperature
- Electrocardiogram (ECG): A QTc interval of > 450 ms confirmed by a second ECG measurement or an otherwise seriously abnormal ECG [47] will be an exclusion criterion for this study. We will only exclude patients if two separate readings are >450ms.
- A QTc interval >500 ms in the ECG or rises by more than 60 msec from baseline or other severe cardiac side effects will stop study participation of this patient.
- A QTc interval >500 ms in the ECG or rises by more than 60 msec from baseline or other severe cardiac side effects in more than one patient in the feasibility study will lead to a stop of the study after the feasibility phase.
- Laboratory parameters: Routine laboratory parameters in patients with AN often show alterations, including electrolytes, liver enzymes, kidney parameters, leukocyte count, haemoglobin and others. Additionally, medical problems secondary to AN, or due to the treatment itself may lead to further laboratory abnormalities [10]. Furthermore, olanzapine may lead to changes in metabolic parameters, including cholesterol, plasma glucose and blood fats [73]. Therefore, the following parameters will

Page 24 of 60

be determined at baseline, 8 weeks, 16 weeks (end of trial medication) and at the 12-month followup.

- Electrolytes and salt/water balance
- Kidney function
- Liver function
- Blood count/bone marrow
- Plasma glucose (fasting or random) or glycated hemoglobin (HbA1c) and lipid profile
- Pregnancy test in women and female adolescents

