4 TRIAL DESIGN

The design of this feasibility study is open treatment of 55 patients with olanzapine for 12 months. Participants will be examined at baseline, and at 8 weeks, 16 weeks, 6 months and 12 months after start of treatment. This is a one-arm open treatment design, there is no placebo and no comparator.

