6.2 Exclusion criteria

Exclusion criteria:

- Serious self-harm, suicidality, psychotic disorder, serious medical comorbidities (as detailed below) which are contraindications for olanzapine
- Current alcohol or illicit drug use disorder
- On major tranquilliser or opioids
- QTc interval >450 ms (two separate ECG measurements) [47]
 - A QTc interval >500 ms in the ECG or rises by more than 60 msec from baseline or other severe cardiac side effects will stop study participation of this patient.
 - A QTc interval >500 ms in the ECG or rises by more than 60 msec from baseline or other severe cardiac side effects in more than one patient in the feasibility study will lead to a stop of the study.

Alerting liver function tests or white blood cell count [47]

- \circ Bilirubin >40 μ mol/L
- Alkaline phosphatase >200 U/L
- AST >80 U/L
- ALT >90 U/L
- GGT >90 U/L
- \circ WBC <2.0 x10⁹/L
- $\circ \quad MCV > 120 \ fL$
- On other psychopharmacological medication at stable dose for <4 weeks
- On medication interacting with olanzapine
- Pregnancy
- Of childbearing potential and unwilling to have pregnancy tests.
- Objecting to taking effective contraceptive measures as specified under section 8.10. on trial restrictions. The participant information and consent sheet include a section on pregnancy and appropriate birth control measures.
- Breast feeding
- Insufficient understanding of the Trial/lack of capacity to agree to the Trial procedures as assessed by the responsible clinician
- Hypersensitivity to Olanzapine or to any of its excipients
- Taking part in another pharmacological trial for AN
- Involvement in research that includes contraindications for treatment with olanzapine

Serious self-harm means one of the following:

• Recent (within the last 12 months) self-harm with suicidal intent

Page 29 of 60

- Recent self-harm with the risk to a person's own life (e.g., drug intake, deep cutting, burning, swallowing sharp items)
- Recent self-harm which could lead, or has led, to long lasting impairment of one's health and functioning

Serious medical comorbidities which are contraindications for olanzapine mean one of the following:

- Coronary heart disease
- Cerebrovascular disease
- Parkinson's disease, parkinsonism or dementia
- Hepatic or renal impairment

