7.10 Withdrawal criteria

The physician responsible for a patient can withdraw a patient from a trial or a certain aspect of the trial any time for appropriate medical reasons, be they individual adverse events or new information gained about a treatment. Trial participants also have the liberty to withdraw their consent at any time and for any reason.

A patient should stop olanzapine treatment if they show:

- If they show a QTc interval >500 ms in the ECG
- If they show rises by more than 60 msec from baseline [47] in the ECG
- Severe cardiac problems
- Serious Adverse Events (SAE) An SAE will be a withdrawal criterion if it is deemed to be related to the treatment with olanzapine by the Principal Investigator
- Serious Adverse Reaction (SAR)
- Suspected Unexpected Serious Adverse Reaction (SUSAR)

However, should a patient stop olanzapine, the patient is not necessary withdrawn from the study, every effort should be made to continue to obtain follow up data as long as the participant is willing.

The whole trial will stop in case of:

- A QTc interval >500 ms in the ECG or rises by more than 60 msec from baseline or other severe cardiac side effects in more than one patient
- Serious self-harm or suicidal behaviour in more than one patient. Serious self-harm is defined as the following:
 - Recent (within the last 12 months) self-harm with suicidal intent
 - Recent self-harm with the risk to a person's own life (e.g., drug intake, deep cutting, burning, swallowing sharp items)

• Recent self-harm which could lead, or has led, to long lasting impairment of one's health and functioning

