7.12 End of trial

The trial will end after the database is locked following the 12 months-assessment of the 55th patient included into the study.

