10.6 Interim analysis and criteria for the premature termination of the trial We do not plan any interim analyses.

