12.2 Peer review

The trial has been peer reviewed a total of 4 times before submission and approval by the NIHR. In February 2017, we applied for the first time in response to the NIHR HTA call 16/97 "Antipsychotics for anorexia nervosa". In this application, we applied for a complete randomised-controlled trial (RCT) including a feasibility study and a main RCT with an in-pilot study. The final time, we applied for a feasibility study only in accordance with the current call 19/76 "Antipsychotics for anorexia nervosa".

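### For the same cardiac trigger in more than one patient, section 3.3.7 defers the stop until after the feasibility phase, while sections 6.2 and 7.10 stop this trial

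*Protocol*

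**What the plan says.** **Trial level.** Section 3.3.7 (Drug safety measures) states that a qualifying cardiac event "in more than one patient in the feasibility study will lead to a stop of the study after the feasibility phase". Section 6.2 (Exclusion criteria) has the matching sentence, but there the event "in more than one patient in the feasibility study will lead to a stop of the study" and the sentence ends. Section 7.10 (Withdrawal criteria) opens its list with "The whole trial will stop in case of" and gives as its first item the same QTc limits or "other severe cardiac side effects in more than one patient".

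**Scope.** Section 4 describes open olanzapine treatment of 55 patients for 12 months and adds: "This is a one-arm open treatment design, there is no placebo and no comparator". Section 7.12 fixes the end: "The trial will end after the database is locked following the 12 months-assessment of the 55th patient". The protocol describes no second phase.

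**Patient level.** For a single patient who meets the trigger, 3.3.7 and 6.2 both end that patient's participation in the study. Section 7.10 instead has the patient stop olanzapine, says that withdrawal from the study does not necessarily follow, and asks sites to do all they can to keep collecting follow-up data for as long as the participant agrees.

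**The concern.** A stopping rule has to tell sites and the data monitoring committee the same thing wherever they look. Here the trigger is identical in three places and the consequence is not. A reader of 6.2 or 7.10 learns that a second affected patient stops the trial. A reader of 3.3.7, the section on safety measurements, learns that the stop comes only once the feasibility phase is over. As nothing follows that phase, the second reader has no stop to apply.

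At stake is whether the remaining participants continue on olanzapine after a repeated cardiac signal. They are aged 12 to 24, and section 6 records that the product information does not recommend the drug under 18 because safety and efficacy data are lacking.

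The patient-level wording raises a smaller issue. If 3.3.7 and 6.2 are followed, the patients who leave follow-up are those with a cardiac signal, whom 7.10 asks sites to keep observing.

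**Working it through.** The protocol gives no figure on this point to reproduce, so the check is a comparison of text.

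**Step 1: is the trigger the same?** Yes. All three sections use QTc above 500 ms, an increase of more than 60 ms over baseline, or another severe cardiac side effect, and all require it in more than one patient.

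**Step 2: is the consequence the same?** No.

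| Section | Consequence of more than one affected patient |
|---|---|
| 3.3.7 | Study stops after the feasibility phase |
| 6.2 | Study stops, with no deferral |
| 7.10 | Whole trial stops |

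**Step 3: can the 3.3.7 deferral take effect within this protocol?** Sections 4 and 7.12 define one single-arm phase that ends at database lock after the last 12-month assessment. A stop placed after that phase comes when no patient is left to stop. Read literally, 3.3.7 halts nothing.

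**Step 4: where might the wording come from?** Section 12.2 records that the first funding application was for a complete RCT "including a feasibility study and a main RCT with an in-pilot study", and that the final one was for a feasibility study only. The deferral would make sense in that larger project. Section 3.3.7 shows another possible sign of older text: its laboratory schedule treats week 16 as the end of trial medication, while sections 4 and 12.11 give a year of olanzapine. That the phrase is left over is an inference; the protocol does not say so.

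**Step 5: does another section settle the matter?** Section 9.3 says that the trial may be discontinued on safety grounds, and the roles section has the monitoring committee advise the steering committee. Both routes are discretionary or advisory. Neither says which of the three statements governs.

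**Step 6: the patient-level wording.** Section 3.7 schedules ECGs at 8 weeks, 16 weeks, 6 months and 12 months. A trigger found at these visits leaves 3, 2, 1 or 0 later assessments whose status depends on the section followed. In the completion proportion one patient weighs 1/55 = 1.8 percentage points, against the 12.2-point margin of error that section 10.1 states for adherence. The effect on estimates is small; the issue is observation of the affected patients.

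**The case against.** The strongest reply is that no real conflict exists. Section 7.10 is the operative section for withdrawal and stopping, and 6.2 agrees with it. Section 3.3 describes outcomes and already holds one forward-looking rule: 3.3.1 keeps poorly completed questionnaires out of any later RCT application. On that model the 3.3.7 sentence could be a bar on proceeding to an RCT, which can coexist with an immediate stop of this trial. This reading is possible, and it lowers the chance that anyone would act on 3.3.7 against 7.10. It does not clear the text. The sentence sits under drug safety, repeats the 6.2 stopping rule almost word for word, and says that the study stops, not that a later study will not start.

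The objection does stand against several stronger inferences.

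- *The trial would run on unnoticed.* The documents do not support this. Two sections require the stop, clinicians report to the chief investigator after each assessment period (10.8), the monitoring committee reviews accruing data, and 9.3 allows discontinuation. What remains is room for delay or dispute.
- *Nearly the whole cohort would be kept on olanzapine.* That is only an upper bound. It needs full recruitment, no other discontinuation, and a second event while everyone else is still on drug. Section 10.1 itself plans on 70% taking the drug for at least 16 weeks.
- *The conflict is likely to arise.* The protocol gives no event rate, so no probability can be stated.
- *Section 10.6 leaves the trial without termination criteria.* It says only that no interim analyses are planned; the criteria are in 7.10 and 9.3.

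On the patient-level point, 7.10 is permissive and depends on the participant's willingness. A specific rule that ends participation after a cardiac event is not strictly incompatible with it, although the request for every effort at follow-up pulls the other way. This part is therefore held with moderate confidence only.

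**Conclusion.** The main point holds with high confidence: the consequence of a second cardiac event is stated incompatibly, and the 3.3.7 version, read literally, has no effect in a protocol with a single phase. It should be corrected, because the rule is a mandatory safety stop in a young population.

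The size is that of an unclear instruction. No sample-size figure, planned estimate or analysis depends on the wording. A reader might infer a statistical flaw, or a trial without effective cardiac protection; neither follows, since the affected patient comes off olanzapine under all three sections, and 6.2 and 7.10 already require the trial to stop.

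The patient-level inconsistency is real but softer, and its numerical effect is small.

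The conclusion assumes that 7.10 states the sponsor's intention. If 3.3.7 was meant as a progression rule, the remedy changes only by one added sentence.

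**What to change.** 1. Make section 7.10 the governing text and delete the closing four words of the trial-level sentence in 3.3.7, so that it matches 6.2.
2. If the sponsor also wants repeated cardiac events to bar progression to an RCT, state this separately as a progression criterion and leave the 7.10 stop as it is.
3. Secondary: in 3.3.7 and 6.2, replace the wording that ends the affected patient's participation with *will stop olanzapine; follow-up continues as in 7.10 if the participant is willing*.

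The cost is a wording amendment to two sections, with one more sentence if item 2 applies. No patients, visits or analyses are added. Item 3 changes what happens to a participant, so the amendment may need notification to the ethics committee. If it is classed as substantial, section 12.10 gives the committee 35 days to respond and requires the NHS R&D office to be notified.

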3.4 Primary endpoint/outcome

Primary objective: feasibility

Primary endpoints: Assessing the proportion of patients in different settings, examining different methods to measure adherence (questionnaire, pill count, olanzapine plasma level). Important measurement time points are the baseline and 12 months after baseline.

Summary statistics will be presented on the following for feasibility and may include estimation of confidence intervals:

Patients approached, screened and included in the study

Adherence, completed physical assessments (including BMI measurement) and questionnaires

Willingness to take part in an RCT

Elements that constitute TAU

Summary statistics on psychopathology, general psychopathology and quality of life assessments and change in BMI will also be reported.

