3.3.6. Drug adherence measures

Olanzapine plasma level: We will perform therapeutic drug monitoring and measure olanzapine levels at week 8 after the start of olanzapine treatment. [70]. An independent physician will have immediate access to olanzapine levels, and feedback to the study team if the level exceeds the upper normal limit. Pill count: We will use the pill count as an indirect measure of adherence. Thus, the number of dosage units that have been taken/not taken will be counted. We are, however, aware that the removal of a dosage unit does not mean that the medication has been taken, that it does not characterize the adherence pattern, and that it is unable to identify causes of adherence or non-adherence. Therefore, we will use pill count in addition to the olanzapine plasma level [71].

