8.9 Concomitant medication

Caution is advised for the drugs listed in the previous section as concomitant medication. However, there is no contraindication for the monotherapy with olanzapine. Additionally, blood concentration of olanzapine will be monitored throughout the study. Contraindications according to the BNF apply to elderly patients who will not be included in this trial and to patients who receive olanzapine as intramuscular application which is not envisaged in this trial either.

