8.11 Assessment of compliance with treatment

Compliance will be assessed by

- Measurement of the olanzapine plasma level 8 weeks after baseline
- Pill count, self-reported by the patient at 8 weeks, 16 weeks, 6 months, and 12 months after baseline.

Noncompliance to the protocol trial procedures will be documented by the investigator. Noncompliance will not lead to withdrawal from the trial. This is a feasibility study which will find out the rate of compliance or noncompliance as well as the rate of participation in assessments and assessment completion.

Compliance and non-compliance are part of the qualitative research aspect of this feasibility study.

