10 STATISTICS AND DATA ANALYSIS

10.1 Sample size calculation

According to the guidance given by the NIHR Research Design Service London, https://www.rds-london.nihr.ac.uk/resources/justify-sample-size-for-a-feasibility-study/, a reasonable sample size can be

Page 44 of 60

between 30 and more than 50 [94,95]. According to the call, our proposed feasibility study should cover: Willingness to accept and adhere to the intervention; a demonstration that adherence can be measured; estimated numbers of young people potentially eligible for recruitment; key parameters of a potential future trial to include a justification of the choice and timing of an appropriate primary outcome measure. Given the variety of parameters, a figure at the upper end of the recommended range seemed plausible to us. We also have also carried out a sample size calculation for this feasibility study based on estimating the feasibility parameter "rate of adherence": Assuming that 70% of patients took olanzapine for at least 16 weeks, a sample size of 55 patients can estimate a 95% confidence interval for this parameter with 12.2% margin of error (i.e., expected CI from 57.8% to 82.2%; for a more extreme attrition rate of 50% the margin of error increases to 13.3%).

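### The adherence part of the primary endpoint cannot be delivered as written: one of its three methods is never scheduled, and the protocol contradicts itself on plasma-level timing and on who does the pill count.

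*Protocol*

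**What the plan says.** Section 3.1 makes adherence to olanzapine part of the primary objective. Section 3.4 turns this into an endpoint and adds time points for the primary endpoints together: "examining different methods to measure adherence (questionnaire, pill count, olanzapine plasma level). Important measurement time points are the baseline and 12 months after baseline". Section 3.2 names the same three methods.

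The operational sections differ:

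- **Plasma level.** Section 3.3.6 will "measure olanzapine levels at week 8 after the start of olanzapine treatment". Sections 3.5, 3.7 and 8.11 also place it at week 8, and 3.5 says so exclusively. Section 8.9 states that "blood concentration of olanzapine will be monitored throughout the study". Section 7.7 includes the level in its list for the 8-week, 16-week, 6-month and 12-month visits with no restriction, although it does restrict other items in that list.
- **Pill count.** Under 3.3.6, "the number of dosage units that have been taken/not taken will be counted". The schedule in 3.7 marks this for the researcher and the clinical team at all four follow-up visits. Section 8.11 has instead: "Pill count, self-reported by the patient at 8 weeks, 16 weeks, 6 months, and 12 months after baseline".
- **Questionnaire.** Named in 3.2 and 3.4 only.
- **Sample size.** Section 10.1 sizes the study on a different time point: "Assuming that 70% of patients took olanzapine for at least 16 weeks".

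**The concern.** Whether patients adhere, and whether adherence can be measured, are main questions of this study; 10.1 records that the funder's call asks for a demonstration of the second. An endpoint that names a method nobody is scheduled to apply cannot be reported in full. An analysis plan cannot repair this, because it cannot analyse data that were not collected.

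The pill-count conflict bears on bias. Section 3.3.6 concedes that an absent tablet is not proof of a swallowed one, and gives this as the reason for pairing the count with a plasma level. Under the schedule the pairing happens once. If the count is also the patient's own report, the later adherence figures have neither an objective measure nor a staff count behind them. Those figures include the 16-week rate that justified enrolling 55 patients. Misreporting of this kind would tend to make adherence look better than it is when a later RCT is planned.

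**Working it through.** **Step 1. Set the sections side by side.**

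| Protocol section | Questionnaire | Plasma level | Pill count |
|---|---|---|---|
| 3.2, 3.4 | named | named | named |
| 3.3.6 | absent | week 8 | units counted, counter not stated |
| 3.5 | absent | week 8 only | not listed |
| 3.7 | no row | week 8 | all four follow-up visits, researcher and clinical team |
| 7.7 | absent | listed for all follow-up visits | listed |
| 8.9 | not addressed | throughout the study | not addressed |
| 8.11 | absent | week 8 | all four follow-up visits, patient-reported |

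**Step 2. Count the methods available at each visit under 3.7.**

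- Week 8: pill count and plasma level, 2 of the 3 named methods.
- Week 16, 6 months and 12 months: pill count only, 1 of 3 at each.
- Baseline: none, since treatment has not begun.

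Methods can therefore be set side by side at 1 of 4 follow-up visits. That visit is neither the 16-week point of 10.1 nor the 12-month point of 3.4.

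**Step 3. Reproduce the precision stated in 10.1.** Inputs from 10.1 are n = 55, assumed rates of 70% and 50%, and a 95% interval. The Wald half-width is 1.96 × √(p(1 − p)/n).

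- With n = 55: 1.96 × √(0.21/55) = 12.1 points, and 1.96 × √(0.25/55) = 13.2 points.
- With n − 1 = 54 in the denominator: 12.2 and 13.3 points, the protocol's own figures.

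The arithmetic is sound. It measures sampling error only and assumes that each patient's adherence is classified correctly.

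**Step 4. Illustrate the error that the margin leaves out.** The protocol gives no misreporting rate, so the following is assumption. Suppose 70% are recorded as adherent and a share s of them are not taking the drug. The true rate is then 70% × (1 − s).

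- s = 5%: 66.5%, a bias of 3.5 points.
- s = 20%: 56.0%, a bias of 14 points.
- The bias equals the stated margin when 70 × s = 12.2, so s = 17.4%.

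Nothing in the protocol says where in this range, or outside it, the study would fall.

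**The case against.** A reader might infer that adherence after week 8 is never verified. The protocol does not support that. Pill counts are scheduled at every follow-up visit and, in 3.7, assigned to staff. Dispensing is scheduled at baseline, 8 weeks, 16 weeks and 6 months. Section 3.3.1 has 12- to 15-year-olds accompanied when taking olanzapine. A subgroup is interviewed about adherence after week 16. What stands is narrower: four sections plan no plasma check after week 8.

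A reader might also infer that the 16-week and 12-month rates rest on self-report alone. That follows from 8.11 but not from 3.7, and the protocol does not say which governs. Nor is week 8 a settled limit for the plasma level, because 7.7 and 8.9 point the other way.

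Two more readings of 3.4 go too far. It speaks of examining methods, not of a formal comparison. Its sentence on baseline and 12 months covers all primary endpoints, some of which do exist at baseline, so it does not claim that adherence is measured there.

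Finally, the 10.1 parameter can be read as staying on treatment, since the same sentence speaks of attrition. Dispensing and withdrawal records can inform that. A pill count and a plasma level together at week 8 may also be enough to show, in a single-arm feasibility study, that adherence can be measured. These points lower the stakes. They do not supply the missing questionnaire or remove the two contradictions.

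**Conclusion.** The concern holds in a limited form. Three defects are certain from the text: a primary endpoint names a questionnaire that is never specified or scheduled; the plasma timing conflicts between 3.3.6, 3.5, 3.7 and 8.11 on one side and 7.7 and 8.9 on the other; and 3.7 and 8.11 disagree on who performs the pill count. The time points in 3.4 also omit week 16, on which 10.1 relies.

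The loss in method coverage assumes that 3.7 is followed. The reliance on patient report after week 8 assumes that 8.11 is followed. The resulting bias cannot be sized from the protocol, and the range shown above is illustration only. No stated precision figure is wrong.

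**What to change.** 1. In 3.2 and 3.4, delete the questionnaire, or name the instrument and add it to 3.7, 7.7 and 8.11.
2. Change 8.11 so that the researcher or clinical team counts the dosage units, in line with 3.7.
3. In 3.4, give adherence its own time points, all after treatment starts and including week 16 to match 10.1.
4. Reconcile the plasma-level timing across 3.3.6, 3.5, 3.7, 7.7, 8.9 and 8.11. The level also serves drug monitoring (3.3.6) and detection of overdose (9.5), so this review does not say which timing is right.
5. If the level stays at week 8 only, limit the examination of methods to week 8 and report later adherence as based on pill count alone.

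The cost is a wording amendment and a little staff time for counting. Assays at the three later visits are optional, at most 55 × 3 = 165. They would first need 3.3.7 and 3.7 reconciled, because 3.7 schedules laboratory tests at 6 months and 3.3.7 does not.
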